**For recipients:****1. Real-time PCR for SARS-CoV-2:**

Nasal swab samples will be taken prior to transfusion and tested for SARS-CoV-2 by real-time PCR method. The test should be positive for eligibility of the recipient along with clinical criteria for COVID-19.

2. Antibody titre: The serum of each recipient will be obtained and IgG antibody titre by enzyme-linked immune-sorbent assay (ELISA) or Rapid IgG antibody method will be tested one day prior to the convalescent plasma transfusion. Changes of IgG antibody titre before and after convalescent plasma transfusion in patients will be studied. The serum will be stored for neutralizing antibody titers by plaque reduction will be done subject to availability.

**Study Population:**

Adult patients with severe COVID -19 infections defined as WHO Interim Guidance and the Guideline of Diagnosis and Treatment of COVID-19 of National Health Commission of China (version 5.0) with confirmation by real-time RT-PCR assay with severe disease i.e. meeting any 2 of the following criteria

1. Patients on ventilator (in last 24 hours)
2. Respiratory distress, RR  $\geq$ 30 beats/min
3. Oxygen saturation level less than 93% in resting state
4. Partial pressure of oxygen (PaO2)/oxygen concentration (FiO2)  $\leq$  300 mmHg
5. Lung infiltrates > 50% within 24 to 48 hours

**Study Design:**

An open label randomized controlled trial.

The study group will comprise of adult patients with severe COVID -19 as detailed above. Randomization will be done in the ratio of 3:1 in with 150 patients in the treatment arm and 50 patients in the control arm. Allocation concealment will be done by Sequentially Numbered Opaque Sealed Envelopes (SNOSE) method.

[name] [name], MD  
Additional Professor - Transfusion Medicine  
Institute of Liver and Biliary Sciences  
[name]  
[name]

### Justification for Unequal Allocation

We want to collect the additional safety profile associated with convalescent plasma group hence enrolling more number of cases in this group.

### Sample Size calculation:

The study will be designed as an open label RCT with an aim to enrol 150 patients in the treatment arm and 50 patients in the control arm.

### Intervention:

**Intervention Arm:** Two doses of 250 ml Convalescent plasma from recovered COVID-19 patients + Standard of Care will be given to severely sick COVID-19 patients in the treatment arm

**Control Arm:** Standard of Care will be given to severely sick COVID-19 patients in the control arm

### Details of Standard of Care

The Ministry of Health and Family Welfare has issued detailed guidelines for the management of sCOVID-19 based on varying grades of severity which may be periodically updated. For the management of ARDS or sepsis the respective guidelines issued by ARDSNet and Surviving Sepsis campaign will be followed. Other institutional protocols for supportive management will be implemented. (ref: Guidelines on Clinical Management of COVID-19. MoHFW, GoI.2020.)

**Monitoring and Assessment:** Daily until clinical improvement

**Adverse Effects:** Will be documented

**Stopping rule:** None

**(C) The expected outcome of the project:** We expect convalescent plasma therapy to be a safe and efficacious therapy based on our pilot RCT. This study will determine if there is clinical improvement /mortality benefits and further elaborate on its safety in patients with severe COVID-19

### Section 14: Inclusion and exclusion criteria for the admission of patients in the study

#### Inclusion criteria

Patients with severe COVID-19 (as described above) will be considered for randomization and will be transfused Convalescent Plasma within 3 days of symptom onset (Severe COVID-19)

**Severe COVID -19 defined** by WHO Interim Guidance and the Guideline of Diagnosis and Treatment of COVID-19 of National Health Commission of China (version 5.0) along with confirmation by real-time RT-PCR assay with severe disease i.e. meeting any 2 of the following criteria-

- Patients on ventilator (in last 24 hours)
- Respiratory distress, RR  $\geq$ 30 beats/min
- Oxygen saturation level less than 93% in resting state

[name] [name], MD  
Additional Professor - Transfusion Medicine  
Institute of Liver and Biliary Sciences  
[name]  
[name]

- Partial pressure of oxygen (PaO2)/oxygen concentration (FiO2) ≤ 300 mmHg
- Lung infiltrates > 50% within 24 to 48 hours

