#### **Transfusion of COVID-19 Convalescent Plasma**

Dose-250 ml

Frequency – 2 doses on consecutive days

Duration –Start by day 3 of symptom onset in eligible patients

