#### **Patient Monitoring**

All included patients will be randomized to receive either 500 ml of convalescent plasma in two doses of 250 ml on two consecutive days along with the standard of care or standard of care alone

Clinical information of all enrolled patients including symptoms at presentation, time to presentation to the hospital, and development of pulmonary symptoms will be recorded. The details of comorbid diseases as measured by the Charlson index of co-morbidity and Acute Physiology and Chronic Health Evaluation II (APACHE II). Details of cross-sectional imaging, chest-x-ray, bacterial or fungal co-infections, and details of antibiotic treatment will be recorded. Development of complications including shock, acute kidney injury, acute coronary syndrome, myocarditis, acute respiratory distress syndrome, need for mechanical ventilation and nosocomial infection will be recorded. The use of high-flow oxygen, non-invasive, and invasive ventilation will follow standard guidelines and will be recorded. The details of antiviral treatment will be recorded for all enrolled patients.

[name] [name], MD  
Additional Professor - Transfusion Medicine  
Institute of Liver and Biliary Sciences  
[name]  
[name]

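### The 3-day onset limit is listed as an inclusion criterion but defined by the plasma transfusion, so it cannot be judged at entry or applied to controls, and two sections disagree on its start and end

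*Protocol*

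**What the plan says.** - **Protocol, Section 14, Inclusion criteria:** patients with severe disease "will be considered for randomization and will be transfused Convalescent Plasma within 3 days of symptom onset (Severe COVID-19". The closing parenthesis names severe COVID-19 as what has its onset.
- **Protocol, Transfusion of COVID-19 Convalescent Plasma:** under the duration item, "Start by day 3 of symptom onset in eligible patients". The severe-disease qualifier is absent here. The same section sets two doses on consecutive days.
- **Protocol, Patient Monitoring:** "All included patients will be randomized to receive either 500 ml of convalescent plasma" or standard of care alone. Inclusion therefore comes before randomisation.
- **Protocol, Intervention:** the control arm receives standard of care and no plasma.
- **Protocol, Study Population and Inclusion criteria:** every patient needs RT-PCR confirmation ("with confirmation by real-time RT-PCR assay with severe disease"; "along with confirmation by real-time RT-PCR assay with severe disease").
- **Protocol, For recipients:** "Nasal swab samples will be taken prior to transfusion and tested for SARS-CoV-2 by real-time PCR method", followed by "The test should be positive for eligibility of the recipient along with clinical criteria for COVID-19".

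**The concern.** An inclusion criterion should be decidable for every patient before allocation, in the same way whichever arm follows. This one is decided by an event after allocation that only the plasma arm can experience. A plasma patient who dies, deteriorates or waits too long for a unit has, read literally, not met an inclusion criterion. An otherwise identical control cannot fail it.

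The trial is open label, so staff will know who missed the limit. The wording invites removing such patients as ineligible, from one arm only, and the randomised comparison would then no longer be protected. Separately, two definitions of onset can lead the two treatment centres to enrol different patients under the same protocol.

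**Working it through.** **1. Plan's own figures.** The protocol gives 150 plasma and 50 control patients: 150/50 = 3 and 150 + 50 = 200, which agrees with the stated 3:1 ratio. No figure in the protocol bears on the window, so the finding rests on comparing the text.

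**2. Can the limit be applied at entry?**

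| Reading of the Inclusion sentence | Plasma arm | Control arm |
|---|---|---|
| Eligibility rule: transfused within the limit | Decided after randomisation | Cannot be applied |
| The limit covers both randomisation and transfusion | Part decided after randomisation | Only the randomisation part applies |
| Treatment instruction only | No limit on time since onset at entry | No limit on time since onset at entry |

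No reading gives an entry rule that is the same in both arms and also limits time since onset, unless the transfusion part is set aside. The time-anchored severity items (ventilation in the last 24 hours, infiltrates over 24 to 48 hours) apply to both arms but do not cap time since onset.

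**3. Start of the clock.** Let symptoms begin on day 0, severe disease on day *s*, and transfusion follow one day later, on day *s* + 1. Counted from severe disease, the delay is 1 day and the limit is met for every *s*. Counted from symptoms, it is met only if *s* + 1 ≤ 3, that is *s* ≤ 2. The two sections therefore agree only for patients who become severe within about two days of first symptoms.

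**4. End of the clock.** One section requires the patient to be transfused within 3 days, the other requires transfusion to start by day 3. With doses on consecutive days, a first dose on day 3 puts the second on day 4. That satisfies the second wording, and fails the first if it means the complete course.

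**5. RT-PCR.** Study Population and Inclusion criteria require confirmation for all patients, and Patient Monitoring has included patients then randomised. A positive test is thus already an entry rule for both arms. The recipients' text places a swab before transfusion and does not say whether it is that entry test.

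**6. Illustration of what exclusion would do.** All rates here are assumed, and there is no treatment effect. A share *f* of patients would miss the limit. They are dropped from the plasma arm only, and all 50 controls are kept. Improvement is *p* = 60% in those who meet the limit and *q* in those who miss it. A binary outcome stands in for time to improvement.

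- Plasma rate after exclusion = *p*; plasma n = 150(1 − *f*)
- Control rate = (1 − *f*)*p* + *fq*
- Spurious difference = *f*(*p* − *q*)

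With *f* = 10% and *q* = 40%, plasma n is 150 × 0.9 = 135, the control rate is 0.9 × 0.60 + 0.1 × 0.40 = 58%, and the difference is 0.10 × 0.20 = 2 points. Each cell gives the spurious difference in points, then the rejection rate of a pooled two-proportion z-test at two-sided 5%:

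| *f* | Plasma n | *q* = 60% | *q* = 40% | *q* = 20% | *q* = 0% |
|---|---|---|---|---|---|
| 5% | 142.5 | 0; 5.0% | 1; 5.2% | 2; 5.8% | 3; 6.7% |
| 10% | 135 | 0; 5.0% | 2; 5.8% | 4; 7.9% | 6; 11.6% |
| 20% | 120 | 0; 5.0% | 4; 7.8% | 8; 16.2% | 12; 30.2% |

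If those who miss the limit do as well as the rest, there is no bias.

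**The case against.** **The sentence may be a treatment instruction.** The transfusion section speaks of patients already eligible and sits beside dose and frequency, so the limit may only tell staff when to transfuse. This is a fair reading. But the sentence stands under Inclusion criteria, and if it is only an instruction, the trial has no entry limit on time since onset. Either way the text needs correcting. The plain symptom onset in the transfusion section may also be shorthand, but nothing in the protocol says so.

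**No exclusion is written.** A reader might infer that plasma patients who miss the limit are removed and that the result will therefore be biased. The protocol does not say this, and analysis sets may be defined in a statistical analysis plan that is not shown. This objection stands, and it makes the figures above conditional.

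**The ways of missing the limit are partly handled.** Plasma is stored in advance, there is a fallback sequence for blood-group matching, and patients with a life expectancy under 24 hours, multi-organ failure or vasopressor need are excluded. This lowers the likely number of failures. It does not remove them, because plasma is held at one site, requested and thawed for patients at other hospitals, and those patients are severely ill.

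**RT-PCR.** A reader might also infer that the positive-swab rule acts after randomisation and in the plasma arm alone. The documents do not support that: confirmation is required of every patient before randomisation, and the recipients' text may simply describe that entry test. Only an unclear sentence remains.

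**Conclusion.** The point holds for the onset window. The only limit on time since onset is tied to an event that follows allocation and happens in one arm, so as written it cannot serve as an entry criterion for both arms. The Inclusion criteria and the transfusion section also disagree on where the clock starts and ends, and must be reconciled. These conclusions follow from the text and need no assumed rate.

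The size of any bias cannot be derived from the protocol. It arises only if patients who miss the limit are excluded and their prognosis differs from the rest. Under the assumed rates, with 5% to 20% dropped, the spurious difference runs from 0 to 12 points and the false-positive rate from 5.0% to 30.2%; the upper end needs one plasma patient in five to be dropped and none of them to improve. If patients with a better prognosis were the ones dropped, the bias would run against plasma. The RT-PCR text needs clarification only.

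**What to change.** - In Section 14, state the timing criterion as time from one defined onset to randomisation, identical in both arms and checked before the envelope is opened.
- Reconcile the Inclusion criteria with the transfusion section on the start and end of the clock. Which onset and what length of window to use is the sponsor's clinical decision.
- If a time limit on transfusion is kept, place it with the treatment instructions and not among the eligibility rules.
- State that missing the transfusion limit, or not being transfused, does not remove a randomised patient from the assigned arm.
- Under For recipients, say that the swab is the pre-randomisation confirmation already required of every patient and not a second gate for plasma recipients.

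**Cost:** wording in three places, with no extra patients or tests. The small downside is that some untransfused patients stay in the plasma arm and slightly dilute the estimate.

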### Section 13: Study Design

#### Aim and Objectives

**Primary Objective:** To study the efficacy of convalescent plasma in severe COVID 19 patients in time to clinical improvement (Clinical improvement: Reduction of two points in ordinal scale or live discharge from the intensive care unit, whichever is earlier)

The six-point scale is as follows:

1. *death=6;*
2. *hospital admission for extracorporeal membrane oxygenation or mechanical ventilation=5;*
3. *hospital admission for non-invasive ventilation or high-flow oxygen therapy=4;*
4. *hospital admission for oxygen therapy (but not requiring high-flow or non-invasive ventilation)=3;*
5. *hospital admission but not requiring oxygen therapy=2;*
6. *discharged or having reached discharge criteria (defined as clinical recovery—ie, normalization of pyrexia, respiratory rate 94% on room air, and relief of cough, all maintained for at least 72 h)=1.*

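### Entry requires neither oxygen support, a minimum ordinal score nor ICU stay, so a ward patient entering at score 2 cannot meet the primary event by recovering and going home

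*Protocol*

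**What the plan says.** Section 13 (Aim and Objectives) makes time to clinical improvement the primary outcome and defines improvement as "Reduction of two points in ordinal scale or live discharge from the intensive care unit, whichever is earlier". There are thus two routes to the event. The six-point scale runs from 6 (death) to 1, and its lower end is:

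- score 3: "hospital admission for oxygen therapy (but not requiring high-flow or non-invasive ventilation)=3"
- score 2: "hospital admission but not requiring oxygen therapy=2"
- score 1: "discharged or having reached discharge criteria", the latter defined by clinical recovery held for at least 72 hours.

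The Study Population paragraph of Section 13 and the Inclusion criteria of Section 14 admit RT-PCR-confirmed patients "with severe disease i.e. meeting any 2 of the following criteria". The five criteria are a ventilator within the last 24 hours, a respiratory rate of at least 30, "Oxygen saturation level less than 93% in resting state", a PaO2/FiO2 ratio of 300 mmHg or less, and lung infiltrates above 50%. Only the ventilator item names respiratory support, and it is optional. The Exclusion criteria set no lower limit on the ordinal score and do not mention oxygen or ICU.

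Study Design plans 150 treated and 50 control patients (3:1). Sample Size calculation repeats these numbers without an effect size, event rate, alpha or power.

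**The concern.** The entry rule and the event definition were not matched. A two-point improvement can be reached only from score 3 or worse, yet the entry rule does not guarantee score 3. The ICU route does not close the gap, because ICU stay is not an entry condition. The protocol also treats ICU stay and hospital stay as different things: they are separate items under Secondary Objectives.

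For a ward patient at score 2 the definition ranks outcomes the wrong way round. Recovering directly and going home is not an event. Deteriorating, entering ICU and leaving it alive is an event. Adjusting for baseline score in the analysis would not help, since it cannot create an event that the definition rules out. Details of Standard of Care also sets assessment as daily until clinical improvement, an end point that this patient does not reach by recovering.

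At stake is a small loss of events, and some sensitivity to where such patients happen to fall, in a trial whose control arm has only 50 patients.

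**Working it through.** **1. Can the two-point route be reached?** Inputs: the scale and event definition in Section 13. The score needed is the baseline score minus 2, and it must be at least 1.

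| Baseline score | Score needed | Reachable |
|---|---|---|
| 5 | 3 | yes |
| 4 | 2 | yes |
| 3 | 1 | yes |
| 2 | 0 | no, the scale stops at 1 |

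This counts the fall from the score at randomisation, which the protocol does not state. If it were counted from the worst later score, a score-2 patient could have the event only by first getting worse. Direct recovery (2 to 1, a one-point fall) is a non-event on either reading.

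**2. Can a patient enter at score 2?** Inputs: the five criteria in Section 14. Any two suffice, so there are 5 × 4 / 2 = 10 minimal pairs.

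- 4 pairs include the ventilator item.
- 6 pairs omit it. Of these, 5 include low saturation or PaO2/FiO2 of 300 or less. Such patients would ordinarily be on oxygen (score 3 or worse), although the text does not say so.
- 1 pair, respiratory rate plus infiltrates, has neither a ventilator nor a hypoxaemia item.

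So 1 of 10 pairs leads clearly to score 2. This counts rules; it does not estimate the share of patients.

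**3. Is the ICU route open?** Only if the patient is in ICU at some time. No entry criterion requires it, so for a patient who stays on the ward it is closed.

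**4. How much could it matter?** The share entering at score 2 and never in ICU is not given. Assumed shares of 2%, 5% and 10% of 200 give 4, 10 and 20 patients. Randomisation at 3:1 would on average place 1, 2.5 and 5 of them in the control arm. Each is 1/50 = 2% of that arm, against 1/150 = 0.67% of the treatment arm. With 10 such patients, 4 falling in the control arm by chance would make 4/50 = 8% of controls against 6/150 = 4% of treated patients.

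The protocol states no power, so there is no planned figure to reproduce. As an illustration, Schoenfeld's formula with two-sided alpha 0.05 gives

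power = Φ(√(d × 0.75 × 0.25) × ln HR − 1.96), with d = 200 × event fraction × (1 − share).

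With an assumed event fraction of 80%:

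| Share with no reachable event | Events d | Power, HR 1.75 | Power, HR 1.5 |
|---|---|---|---|
| 0% | 160 | 86.5% | 60.3% |
| 2% | 157 | 85.9% | 59.4% |
| 5% | 152 | 84.8% | 58.1% |
| 10% | 144 | 82.8% | 55.8% |

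The first row at HR 1.75 is √30 × 0.560 − 1.96 = 1.105, and Φ(1.105) = 86.5%. The table counts lost events only and holds the hazard ratio fixed. Patients without a reachable event in both arms would also pull the observed ratio slightly towards 1.

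**The case against.** The strongest reply is that few patients, if any, will be affected. To enter at score 2 through the one clear pair, a patient needs a respiratory rate of at least 30 and infiltrates above 50%, yet saturation of 93% or more, PaO2/FiO2 above 300 (a lower value would itself suggest a need for oxygen), no oxygen requirement, and no ICU stay afterwards. Severity is also tied to outside guidance, and the need for oxygen is governed by national guidelines and an annexure, none of which is shown. The secondary outcomes include duration of oxygen therapy and of ICU stay, which suggests that a population on oxygen and in ICU was in mind.

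Most of this stands as an argument about size. It does not close the gap: the five criteria are given as the working definition of severe disease, and what the authors had in mind is not an entry rule.

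Three stronger readings are tempting, and the protocol does not support them.

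- *Every patient entering at score 2 is unable to have the event.* A score-2 patient in ICU has it on leaving ICU alive.
- *Going home counts as treatment failure.* The outcome is a time to improvement. Such a patient has no event, and the protocol does not say how that is handled.
- *Patients weaned from a ventilator within the last 24 hours form a second clear group at score 2.* The ventilator criterion can also mean ventilation begun in that period. A patient just weaned may still be in ICU, with the second route open.

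**Conclusion.** The point holds in a limited form. On the literal text, a ward patient can enter at score 2 and then recover fully without meeting either route of the primary event. This follows from Section 13 and Section 14 alone and needs no outside assumption.

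Its size does rest on assumptions. The share affected is unknown and probably small. At an assumed 2% to 10%, power falls by about 0.6 to 3.7 percentage points at HR 1.75 (86.5% to 85.9% or 82.8%) and by 0.9 to 4.5 points at HR 1.5, if 80% of the other patients have the event.

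A reader might infer that the result would be biased. That does not follow: randomisation spreads these patients over both arms in proportion, so what remains is slight dilution and chance imbalance. The case for correcting it is that the mismatch is in the primary event itself and the remedy is almost free.

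**What to change.** In Section 13 (Aim and Objectives), keep both existing routes and add a third, so that the event reads in substance: *a fall of two points on the ordinal scale, or reaching score 1, or leaving the intensive care unit alive, whichever comes first*. The third route should name score 1 as the scale defines it, including patients who meet the discharge criteria but are still in hospital, and not hospital discharge alone. The ICU route must not be dropped in the rewording.

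Nothing changes for baseline scores 3, 4 and 5, where reaching score 1 is already a fall of 3 − 1 = 2, 4 − 1 = 3 or 5 − 1 = 4 points. For baseline 2, recovery becomes an event. No new data are needed, because the date of reaching score 1 is already required for patients who enter at score 3.

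An optional alternative is to limit entry to scores 3 to 5 in the Study Population paragraph and in Section 14. This closes the gap at source but makes a few patients ineligible, and it is not needed if the endpoint phrase is added.
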